2.2.2 Randomization and Blinding

This is an open label study. There is no randomization and all subjects and study personnel are unblinded. All subjects who enroll in this study will receive tenapanor 50 mg BID.

2.2.3 Duration of Study

For each subject, the entire study will last for a total of approximately 52 to 55 weeks; including completion of either the TEN-01-301 or TEN-01-302 studies. For subjects completing studies TEN-01-301 or TEN-01-302, TEN-01-303 treatment duration will be 39 and 26 weeks, respectively. The study flow chart, including all procedures to be performed during the study is presented below.

SCHEDULE OF ASSESSMENTS FOR THE STUDY

The study flow chart, including all procedures to be performed during the study is presented below. Prior to engaging in any study procedure, each subject must sign and date an informed consent form. In addition, a telephone contact will take place as footnoted below to find out if any treatment related problems have occurred. Additional telephone calls to the subjects for treatment follow-ups of AEs will be made as needed.

Evaluation	Enroll ^a	Treatment Period		
		1	2	3 ^b
Site Visit ^h	1	2	3 ^b	4/ET ^c
Study Week	1	13±2	26±2	39±2
Informed Consent ^a	X			
Inclusion/Exclusion	X			
Concurrent Medications		X	X ^{b#}	X
Physical Exam			X ^b	X
Vital Signs ^d		X	X ^{b#}	X
Clinical Laboratory Tests ^f			X ^b	X
Urine Pregnancy test ^{fg}		X	X ^{b#}	X
Urinalysis ^f			X ^b	X
12-lead ECG			X ^b	X
Drug Dispensed/returned	D	D/R	D [#] /R ^{b#}	R
Adverse Event Assessments		X	X ^{b#}	X

^a The Informed Consent Form (ICF) must be signed before any protocol procedures are performed.

^b This is the final visit for subjects who enrolled from Protocol TEN-01-302 and only procedures with this footnote are performed. Procedures for subjects enrolled from Protocol TEN-01-301 are marked with a #.

^c This is the final visit for subjects who enrolled from Protocol TEN-01-301.

^d Vital signs include systolic and diastolic blood pressure (seated), heart rate, respiratory rate, temperature and body weight.

^e When a subject discontinues early, procedures performed at Visit 4 should be performed at the subject's last visit.

^f Laboratory assessments are detailed in Appendix A of the protocol.

^g If the urine pregnancy test is positive, it will be confirmed with a serum pregnancy test.

^h Telephone calls will be made to subjects monthly during the two months prior to a site visit to ascertain if there have been any treatment related problems (Weeks 5±1, 9±1, 17±1, 22±1, for subjects from TEN-01-301 and TEN-01-302 and for subjects from TEN-01-301 also Weeks 30±1 and 35±1).

2.3 Safety Variables

Safety variables will include adverse event (AE) reporting throughout the trial, clinical laboratory tests (serum chemistry, hematology, and urinalysis), vital signs (including body weight body mass index [BMI]), 12-lead ECGs, and physical examinations.

3. STATISTICAL METHODOLOGY

3.1 Determination of Sample Size

Based on the two Phase 3 studies (TEN-01-301 and TEN-01-302) and the different treatment arms, 300 subjects entered into this open label long-term safety study should produce approximately 150 subjects with at least 52 weeks exposure to tenapanor 50 mg BID and an additional 150 subjects with 26 to 39 weeks of exposure to tenapanor 50 mg BID.

3.2 Analysis Sets

Safety Analysis Set: All subjects who receive at least one dose of study drug will be included in all analyses of safety data.

3.3 Procedures for Handling Missing Data

The safety analysis will be based on the observed data. Except for provisions for estimating the date of the last dose ([Section 3.6.4](#)), no imputations or carried forward analyses will be performed.

3.4 Methods of Pooling Data

Other than the treatment cohorts described below, no data will be pooled for purposes of analyses.

3.5 Visit Windows

Observed data will be used for the safety analyses. No visit windows will be applied.

3.6 Statistical Analyses

Summary tabulations will be presented which will display descriptive statistics by visit for five treatment cohorts and for all subjects in the safety analysis set. These treatment cohorts are identified below.

Treatment Cohorts for Summary Tabulations

Cohort	Protocol 301		Protocol 303
	12-Weeks	4-Weeks	39-Weeks
1	Tenapanor 50 mg BID	Tenapanor 50 mg BID	Tenapanor 50 mg BID
2	Tenapanor 50 mg BID	Placebo	Tenapanor 50 mg BID
3	Placebo	Tenapanor 50 mg BID	Tenapanor 50 mg BID
	Protocol 302		
	26-Weeks		26-Weeks
4	Tenapanor 50 mg BID		Tenapanor 50 mg BID
5	Placebo		Tenapanor 50 mg BID

The number of observations, mean, standard deviation, minimum, median, and maximum values will be displayed for continuous variables, and the number and percent of subjects per category will be displayed for categorical data.

As this is an open label study of only treatment with tenapanor 50 mg BID, no statistical testing will be performed.

3.6.1 Subject Disposition

Subject disposition information will be summarized by treatment cohort and all subjects overall. The number and percent of subjects who are enrolled, who took a dose of study drug, who complete the study, and who withdraw early from the study will be presented. The primary reason for early withdrawal will also be tabulated. The number of subjects enrolled will be used as the denominator for the percentage calculation. Subject disposition, inclusion / exclusion criteria, and protocol deviations will be listed.

The number and percent of subjects in the safety analysis set will also be tabulated.

3.6.2 Demographic and Background Characteristics

Demographic and background characteristics from TEN-01-301 and TEN-01-302 will be summarized by treatment cohort and all subjects overall. Variables included in this assessment will be the demographic characteristics of age at informed consent (years), gender, race, ethnicity, body weight (kg), and BMI (kg/m²).

Medical history and gastrointestinal (GI) history from TEN-01-301 and TEN-01-302 will be summarized for the number and percentage of subjects for each body system. Medical history includes verbatim terms recorded for the subjects. GI history includes duration (years) since IBS symptoms began before enrollment, duration (months) since last colonoscopy before enrollment, and whether colonoscopy findings are not significant. Medical and GI history will also be listed.

3.6.3 Concomitant Medication

All medications administered during this study will be considered concomitant. These medications will be coded using the latest available version of the World Health Organization (WHO) Drug Reference List. The number and percentage of subjects taking concomitant medications will be summarized by Anatomical Therapeutic Chemical (ATC) class and preferred name by treatment cohort and all subjects overall.

A listing of all medications including the reported term, preferred name, ATC class, start and stop dates, and other relevant data will be provided.

3.6.4 Study Drug Exposure and Compliance

Days of exposure to study drug will be summarized with descriptive statistics by treatment cohort and all subjects overall. In addition, a contingency table will be provided to display the number and percentage of subjects in each treatment cohort and overall with exposure in the following categories: ≤ 13 weeks, >13 to ≤ 26 weeks, and >26 weeks.

Days of possible exposure is defined as:

$$\text{date of last dose of study drug} - \text{date of first dose of study drug} + 1.$$

When the last known dose date is missing, the last known clinic visit date during the treatment period will be used, and the plus 1 will be removed from the calculation.

Summary statistics will also be presented for percent compliance to study drug. The percent compliance to study drug will be calculated as the total number of tablets dispensed minus the total number of tablets returned divided by two times the number of days during the treatment period, then multiplied by 100.

Summary statistics will be presented for percent compliance to study drug by treatment cohort and overall. The count and percentage of subjects with overall compliance $<80\%$, $80\%-100\%$, and $>100\%$ will also be tabulated by treatment cohort and overall.

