10. STATISTICAL CONSIDERATIONS

This open label long-term safety study will evaluate the safety of tenapanor in subjects with constipation predominant IBS (IBS-C) who have completed either study TEN-01-301 or TEN-01-302. Approximately, 300 subjects who qualify will be enrolled at approximately 50-60 US clinical centers and receive tenapanor 50 mg BID for up to 52 weeks total (previous protocol and this study).

. A statistical analysis plan (SAP) will be developed, finalized, and signed-off on prior to the database lock. This plan will confirm the analysis sets used in the analysis, outline all data handling conventions, and specify all statistical methods to be used for all safety analyses. A set of table, listing, and figure shells will also be part of this plan for internal use. Any changes to the statistical considerations described in Section 10 of this protocol will be addressed in the SAP and will not be part of a protocol amendment.

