10.7.4 Study Drug Exposure and Compliance

Days of exposure to study drug will be summarized with descriptive statistics by treatment cohort and all subjects overall. Summary statistics will also be presented for percent compliance to study drug. The percent compliance to study drug will be calculated as the total number of tablets dispensed minus the total number of tablets returned divided by two times the number of days during treatment, then multiplied by 100.

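### SAP 3.6.4 counts unreturned tablets as taken but, with no last dose date, ends exposure at the last clinic visit: a lost subject can score 209% compliance or 0 exposure days

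*SAP*

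**What the plan says.** SAP 3.6.4 defines days of possible exposure as last dose date minus first dose date plus 1. With no last dose date recorded, "the last known clinic visit date during the treatment period will be used, and the plus 1 will be removed from the calculation". No lower limit is given.

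The same section gives percent compliance as follows: "total number of tablets dispensed minus the total number of tablets returned divided by two times the number of days during the treatment period", times 100. Protocol 10.7.4 has the same numerator, "divided by two times the number of days during treatment, then multiplied by 100". The SAP also promises a table: "The count and percentage of subjects with overall compliance" below 80%, from 80% to 100%, and above 100%, by cohort and overall.

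Protocol 6.3 and SAP 2.2.1 say that subjects will be asked at each visit to return unused drug and bottles. Neither document has a rule for bottles that do not come back. SAP 3.3 says that, apart from estimating the last dose date, "no imputations or carried forward analyses will be performed". SAP 3.2 defines the safety set by dosing: "All subjects who receive at least one dose of study drug will be included in all analyses of safety data".

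**The concern.** The numerator and denominator can cover different stretches of time. At Visit 2 (and Visit 3 for TEN-01-301 subjects) a new supply is added to tablets dispensed. If the subject is then lost, nothing from that supply is returned, so all of it is scored as swallowed. The exposure fallback, meanwhile, ends the days on the date that supply was handed out. The subject about whom least is known therefore gets one of the highest compliance values.

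A retained bottle has a similar effect without loss to follow-up, and can move a poorly adherent subject into the top category. On the exposure side, a subject known to have taken drug can be tabulated with 0 days.

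At stake are the compliance summary and its three-category table, and the minimum and mean of exposure. Protocol Section 10 says the SAP will "outline all data handling conventions, and specify all statistical methods to be used for all safety analyses", so these conventions belong there.

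**Working it through.** The documents state no compliance or exposure result, so there is no figure to reproduce. The stated rules can be run on simple cases.

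**Inputs**
- 66 tablets per bottle (Protocol 6.2) and three bottles per dispensing (Protocol 6.3, SAP 2.2.1): 3 × 66 = 198 tablets.
- Two tablets a day. Thirteen weeks is 91 days, so 182 tablets are due and 198 − 182 = 16 are left over.
- Assumptions: visits fall on the nominal week, the first dose is on the day of Visit 1, and compliance days equal exposure days.

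**1. Fully adherent to Week 13, then lost, no last dose date.** Dispensed 2 × 198 = 396; returned 16; fallback exposure 91 days.
(396 − 16) / (2 × 91) = 380/182 = 208.8%. Adherence over those 91 days was 182/182 = 100%.

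**2. TEN-01-301 subject, fully adherent to Week 26, then lost.** Dispensed 3 × 198 = 594; returned 16 + 16 = 32; exposure 182 days.
(594 − 32) / (2 × 182) = 562/364 = 154.4%, against a true 100% to Week 26.

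**3. One full bottle kept at Week 13 by a subject whose treatment ends there.** Tablets taken 198 − 66 = 132, so true compliance is 132/182 = 72.5%. Nothing is returned, so the formula gives 198/182 = 108.8%. The subject moves from below 80% to above 100%.

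**4. Dosed, last dose date missing, no clinic visit after Visit 1.** Visit 1 date minus first dose date, without the plus 1, is 0 days. A subject with one known dosing day gets 1. The Week 5 and Week 9 contacts are telephone calls, not clinic visits, so someone on drug at the Week 9 call (roughly 57 to 63 days) would still have 0. Compliance then divides by zero.

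**5. Sensitivity to the denominator.** On planned days (182 for TEN-01-302, 273 for TEN-01-301), case 1 gives 380/364 = 104.4% or 380/546 = 69.6%, and case 2 gives 562/546 = 102.9%. The large figures therefore depend on exposure days being the denominator. The numerator still includes tablets of unknown fate either way.

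**6. The proposed rule on the same cases.** Case 1: (198 − 16)/(2 × 91) = 100%. Case 2: (396 − 32)/(2 × 182) = 100%. Case 3: not evaluable. Case 4: 1 exposure day, compliance not evaluable. A subject who stops on day 30 and returns all remaining drug on day 60: (198 − 138)/(2 × 30) = 60/60 = 100%.

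**The case against.** The formula is determinate, and counting unreturned tablets as taken is a familiar limit of pill counts. Values above 100% get their own category, so they are visible. Withdrawing subjects should have the Visit 4 assessments and monthly calls are scheduled, so the 0-day case needs several things to go wrong together. The fallback is worded for a missing last *known* dose date. Since anyone with a first dose date has one known dose date, it may apply to fewer subjects than it seems. The stand-alone programming specifications (SAP Section 4), which are not in the documents, may settle all of this.

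Much of that stands, and it limits the point to a minor one. It does not remove the mismatch. A category above 100% does not separate over-use from missing bottles, and case 3 shows a subject who belongs below 80% placed there. If *known* was meant to narrow the fallback, the SAP should say so; read strictly, the clause would have almost nothing to do.

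Stronger readings are tempting but not supported:
- *Exposure of −1 day.* This needs a first dose the day after Visit 1. No passage excludes that, but none states it.
- *No exposure value at all.* This needs Visit 1 to lie outside the treatment period, and rests on a schedule header broken in text extraction.
- *A denominator undefined for everyone.* SAP 2.2.3 says "TEN-01-303 treatment duration will be 39 and 26 weeks, respectively", so a reader might divide by planned days and score a fully adherent Week 13 withdrawal at 182/364 = 50% or 182/546 = 33%. The protocol's wording and the exposure definition just above the formula point to exposure days. One clarifying phrase is enough.
- *Compliance set to missing under SAP 3.3.* A ban on imputation does not displace a formula that can be computed from the recorded counts.

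**Conclusion.** The concern holds for subjects with unreturned drug, and for dosed subjects with no last dose date and no clinic visit after Visit 1. Followed as written, SAP 3.6.4 gives 209% or 154% for subjects who were exactly adherent until lost, 108.8% for one who was 72.5% adherent, and 0 exposure days for someone who was dosed. These are per-subject figures that rest on the assumptions listed with the inputs.

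Severity is minor. The study is descriptive with no testing, adverse event percentages use subject counts, and 0 days still falls in the lowest exposure category (up to 13 weeks). The documents do not say how many subjects would be affected. It could be near zero, so no effect on cohort means is claimed.

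**What to change.** Amend SAP 3.6.4 as follows.

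1. State that compliance days are the days of possible exposure, with a minimum of 1 day for every subject in the safety set.
2. Compute compliance only over dispensing intervals with a complete return count (all bottles back, empty or not). Interval days run from the dispensing visit, or the first dose if later, to the next visit or the last dose, whichever is earlier. Count a visit day once, in the interval it opens, and count the day of the last dose. Exclude both the tablets and the days of any other interval.
3. Report subjects with no complete interval as not evaluable, and show the number of subjects with unreturned bottles beside the three-category table. Keep the literal formula as a supplementary summary if wanted.

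The cost is a few sentences and minor programming, using visit dates and return counts that the sites already collect. There are two drawbacks. Some compliance values become not evaluable, and the estimate rests on the better-documented intervals, which may be the more adherent ones; the supplementary summary and the count of unreturned bottles let a reader judge that. The 1-day minimum removes an impossible value but does not recover true exposure.

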3.7 Safety Analyses

Safety assessments will be based on the incidence, severity, and type of adverse events, and clinically significant changes in the subject's clinical laboratory tests, vital signs, ECGs, and physical examinations.

3.7.1 Adverse Events

Adverse events will be coded using the MedDRA adverse event coding system for purposes of summarization. All adverse events reported will be listed in the data listings. Treatment emergent adverse events (TEAEs) will be tabulated for each treatment cohort and overall. A treatment-emergent AE (TEAE) is any AE that starts on or after the first dose of study drug through the final visit (Visit 3 for subjects from TEN-01-302 and Visit 4 for subjects from TEN-01-301), any event that is considered drug related regardless of the start date, or any event which occurs prior to the first dose of study drug and worsens in severity or is

subsequently considered drug-related by the investigator. An AE is considered drug related if it is possibly related or probably related to study drug.

TEAEs will also be tabulated by whether events are considered related to treatment and by severe severity. Serious adverse events (SAEs) and TEAEs resulting in study discontinuation will be tabulated.

Summarization of AEs will include subject incidence of the following:

- All TEAEs
- Drug-related TEAEs
- Severe TEAEs
- Severe and drug-related TEAEs
- SAEs
- Drug-related SAEs
- Death due to AEs
- TEAEs leading to study drug discontinuation
- Drug-related TEAEs leading to study drug discontinuation

An overall summary table will contain the number and percentage of subjects ever having one of the above listed subsets of AEs. All TEAEs will be summarized for each treatment cohort and overall by MedDRA system organ class (SOC), by SOC and preferred term (PT), and by PT with the number and percentage of subjects. If a subject has more than 1 occurrence of the same TEAE, he/she will be counted only once within that preferred term and system organ class in the summary tables. The most severe occurrence of a repeat TEAE, as well as the closest relationship of the TEAE to the study drug will be used for the analyses.

TEAEs related to study drug, severe TEAEs, SAEs, and TEAEs leading to study drug discontinuation will be summarized in the same manner. That is, summaries will be provided for the numbers and percentages of subjects by SOC, SOC and PT, and PT.

All AEs will be included in by-subject listings. Specific by-subject listings of SAEs and TEAEs leading to study drug discontinuation will be provided. The number of days between first dose and when the event occurred will be presented in listings as well (i.e., relative study day), as will duration of the AE.

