9. ADVERSE EVENTS

9.1. Adverse Event

An **adverse event** (AE) is any untoward medical occurrence in a subject administered a pharmaceutical product, whether or not the occurrence has causal relationship with this treatment. An adverse event can therefore be any unfavorable and unintended sign (including an abnormal laboratory finding), symptom, or disease temporally associated with the use of an investigational product, whether or not considered related to the investigational product. This includes any newly occurring event or previous condition that has increased in severity or frequency since the administration of the investigational product.

Worsening of IBS symptoms is not considered an adverse event unless the frequency and/or severity of the symptom(s) are outside of what the subject considers normal for their IBS.

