10.7.5 Safety Analyses

Safety assessments will be based on the incidence, severity, and type of adverse events, and clinically significant changes in the subject's clinical laboratory tests, vital signs, ECGs and physical examinations.

Adverse events will be coded using the MedDRA adverse event coding system for purposes of summarization. All adverse events reported will be listed in the data listings. Treatment emergent adverse events (TEAEs) will be tabulated for each treatment cohort and overall, where treatment emergent is defined as any adverse event which occurs after administration of the first dose of study drug and up through the final visit (Visit 3 for subjects from TEN-01-302 and Visit 4 for subjects from TEN-01-301), any event that is considered drug-related regardless of the start date of the event, or any event that is present at baseline but worsens in severity or is subsequently considered drug-related by the investigator. TEAEs will also be tabulated by whether events are considered related to treatment (possibly or probably drug-related, or unknown in relationship) and by severity. Serious adverse events and TEAEs resulting in study discontinuation will be tabulated.

Actual values and change from baseline values for clinical laboratory tests (including urinalysis) will be summarized at each visit collected during the study for each treatment cohort and overall. The frequency of clinically significant abnormal laboratory test values will be tabulated by treatment cohort and overall. Shift tables will be derived for changes in laboratory tests from the last values obtained during TEN-01-301 or TEN-01-302 to Visit 3 or 4.

Vital signs will be summarized descriptively for actual values and change from baseline values by visit and treatment cohort as well as overall. Vital signs are collected at study visits 2, 3 and 4, as applicable. Baseline for the vital signs will be the last values obtained during TEN-01-301 or TEN-01-302.

12-lead electrocardiogram (ECG) results will be summarized descriptively for actual values and change from baseline values by treatment cohort and overall for each visit (Visit 3 or Visit 4 as applicable). Baseline for the ECG will be the last values obtained during TEN-01-301 or TEN-01-302. The overall interpretation will be

summarized with number of subjects and percentages for the normal and abnormal ECG result categories.

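### The worsening clause of the TEAE definition (Protocol 10.7.5, SAP 3.7.1) names severity only, so an unrelated pre-dose event that becomes more frequent can be an adverse event under Protocol 9.1 without being a TEAE

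*SAP*

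**What the plan says.** Protocol 9.1 defines an adverse event and extends it to conditions that were already there: "This includes any newly occurring event or previous condition that has increased in severity or frequency since the administration of the investigational product". For IBS symptoms it applies the same double test. Worsening is not an adverse event "unless the frequency and/or severity of the symptom(s) are outside of what the subject considers normal for their IBS".

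The TEAE definition is given twice. Protocol 10.7.5 includes "any event that is present at baseline but worsens in severity or is subsequently considered drug-related by the investigator". SAP 3.7.1 includes "any event which occurs prior to the first dose of study drug and worsens in severity", with the same alternative of a later judgement that the event is drug related. Neither definition mentions frequency.

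SAP 3.7.1 builds its incidence tables by system organ class and preferred term mainly on TEAEs. SAEs and deaths have their own summaries, which are not worded as limited to TEAEs. All adverse events go into by-subject listings.

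**The concern.** The protocol counts two kinds of worsening as adverse events, and the treatment-emergent rule carries only one of them forward. Neither document gives a reason for leaving frequency out.

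Safety is the only objective, there is no concurrent comparator and no testing is planned, so the TEAE incidence tables are a main result of the study. All subjects have IBS-C and come from a parent study of 16 or 26 weeks, so some may have an ongoing condition at the first dose here. Cohorts 2 and 5 move from placebo to tenapanor on entry. The severity scale in Protocol 9.2 grades impairment of functioning, so an event can become more frequent without changing grade. Where that happens, whether it reaches the TEAE tables depends on the causality call and on how the site dates the record.

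**Working it through.** The point concerns definitions, and the plan gives no figure to reproduce. The check is to take one case through every route in SAP 3.7.1. The case is an event present before the first dose, more frequent afterwards, at the same severity grade. I take the first dose to be the first dose in TEN-01-303.

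The routes are:

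1. Onset on treatment: "any AE that starts on or after the first dose of study drug through the final visit".
2. Drug related, any onset: "any event that is considered drug related regardless of the start date". The SAP adds: "An AE is considered drug related if it is possibly related or probably related to study drug".
3. Pre-dose onset, with either (a) worsening in severity or (b) the event being "subsequently considered drug-related by the investigator".

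Applied to the case:

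| How the increase is judged and recorded | Route met | In TEAE tables? |
|---|---|---|
| Possibly or probably related | 2 and 3(b) | Yes |
| Not related, entered as a new event dated on or after first dose | 1 | Yes |
| Not related, kept under its pre-dose start date | None: 1 fails on date, 2 and 3(b) on causality, 3(a) on grade | No |

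Protocol 10.7.5 has equivalent routes and gives the same result in all three rows. Only the third row is lost. By Protocol 9.1 it is an adverse event; by both TEAE definitions it is not treatment-emergent.

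The second and third rows can describe the same clinical course. They differ only in the start date entered, and neither document says which date to use when frequency rises. Protocol 8.2.1.1 and 9.7 only ask that events be followed until they resolve or are explained by a stable or chronic condition or a concurrent illness.

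On size, the documents give only the planned number of 300 subjects (Protocol 5.1 and 10.1). Purely as assumptions, suppose 10% to 20% of subjects enter with an ongoing event and 10% to 30% of those become more frequent without a grade change:

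- Low: 300 × 0.10 × 0.10 = 3 subjects, 3/300 = 1.0%.
- High: 300 × 0.20 × 0.30 = 18 subjects, 18/300 = 6.0%.

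These are gross counts. If a fraction r of them is judged related or entered as a new event, the net number is the gross number × (1 − r). Nothing in the documents fixes r between 0 and 1, so under these assumptions the net number lies anywhere from 0 to 18. A subject with another TEAE would still count in the any-TEAE line, although the row for the missed preferred term could be short by one.

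**The case against.** Four objections deserve weight.

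First, a reader might infer that the plan admits only worsening in severity, so that every increase in frequency disappears from every TEAE table. The documents do not support that. Routes 2 and 3(b) bring in any event judged related, and route 1 brings in any increase recorded as a new event.

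Second, a reader might infer that the SAP departs from the protocol. It does not: Protocol 10.7.5 has the same severity-only clause. The mismatch is between Protocol 9.1 and the TEAE definition in both documents.

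Third, because Protocol Section 2 describes a drug that raises luminal fluid and stimulates motility, one might infer that the rule loses the very effects the drug is expected to cause. Protocol 9.4 points the other way. An event can be possibly related on timing or on a known response pattern, even if the underlying condition could explain it. More frequent bowel events on drug fit that description and would then be TEAEs. It is still true that the not-related category names the subject's clinical condition as an alternative cause, so the call is not automatic. An all-causality table should not depend on it.

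Fourth, the lost case needs a record in this study with a pre-dose start date. Protocol 9.6 begins reporting at Day 1, Visit 1 has no adverse event assessment, and neither document says that ongoing parent-study events are entered. Protocol 9.1 can also be read as dating the event from the increase. This narrows the gap. It does not close it: both TEAE definitions provide for events that begin before the first dose, and no start-date rule is stated.

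The study is also descriptive and the missed events remain in listings. That limits the consequence but does not remove the inconsistency.

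**Conclusion.** Wrong as written (internal inconsistency), minor. A pre-existing event that becomes more frequent after the first dose at the same grade, is judged not related and keeps its pre-dose start date is an adverse event under Protocol 9.1. It is still missed from the TEAE tables. It appears only in listings, or in the SAE or death summaries if it qualifies for them.

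Any effect on TEAE incidence is downward, but its size is unknown and may be close to nothing. The range of 3 to 18 subjects rests wholly on assumed rates and is taken before any deduction, so it should not be read as an estimate of bias. The conclusion itself needs no rate. It needs only that sites may leave such an event under its pre-dose date, and nothing in the documents prevents that.

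**What to change.** In SAP 3.7.1, have the worsening clause cover an event that begins before the first dose and then worsens in severity or frequency. Protocol Section 10 says that changes to its statistical considerations are handled in the SAP without a protocol amendment, so the Protocol 10.7.5 wording does not have to be amended first.

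In the eCRF guidance, tell sites to record such an increase as a new adverse event with the date of the increase as its start date. Neither document says that the event record captures frequency, so without this instruction the revised clause may have nothing in the data to act on. It can help only for events still to be recorded.

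Nothing about seriousness needs adding to the clause, because SAEs are tabulated separately.

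The cost is one clause, one line of site guidance and slightly higher TEAE percentages. New records will not inflate the subject counts through repeats, since SAP 3.7.1 counts each subject once per preferred term and system organ class.
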